SPECIFIC AIM: To pilot test the intervention in engaging HIV- WWIDs in PrEP by integrating it into the health care services of a syringe exchange to assess promise of efficacy. To address Aim three we will: 1. Conduct a pilot test with WWIDs (n=68) randomized to an “Enhanced” intervention that includes targeted PrEP messages in counseling, materials, and text messages compared to a “Basic” intervention that includes general messages in counseling, materials, and text messages. To assess promise of efficacy, we will compare PrEP adherence (biomedical testing, self-report) at one month, end and three-month follow-up and assess differences in self-reported PrEP attitudes, self-efficacy and decisional conflict.

Role of Principal Investigator

[name] - [name] is the PI for the project and will oversee all operations. She is responsible for designing instruments, overseeing research assistants, conducting analysis for perceptual mapping and vector analysis, modeling messages and applying them in order to assess for cultural salience and receive insight into potential intervention strategies with women who inject drugs. She will oversee recruitment, data collection, monitor safety and human subject issues and facilitate communication between and among study staff and study site. She will also monitor the study budget and expenditures. As PI she will oversee all aspects of the project to ensure successful completion.

Study Objectives

The main objective of this study is to pilot test a randomized intervention to increase uptake and adherence to PrEP in women at risk of HIV who are clients of Prevention Point Philadelphia, a needle exchange program.

If successful, the proposed pilot study will significantly contribute to HIV prevention by examining the unique perceptions of PrEP in WWIDs and the acceptability, feasibility, and

potential impact of using health communication strategies in adjunct with existing services in a social service agency.

Background

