Prevention Point Philadelphia (PPP). PPP is the only syringe exchange in Philadelphia. They promote health, empowerment and safety for communities affected by drug use and poverty by offering case management, syringe exchange, medical services, HIV and Hepatitis C (HCV) testing, addiction services, housing services, free meals, legal clinic and overdoes prevention and reversal training. PPP serves hundreds of people throughout the week, many of whom attend almost daily.

Sampling

Subjects will be screened for their interest in and eligibility for participating. We aim to enroll 68 women, assuming a 75% retention rate at the end of the intervention, leaving us a final study sample of 50. Treatment allocation will be accomplished using randomization through REDCap, a HIPAA approved research management software.

PROCEDURE PHASE 3

For graphic representation of study Procedure, see attached. Participants will be asked to participate after or while waiting for services at the study site. If they are interested, research staff will take participants into a designated private room and ask eligibility questions and be HIPAA consented. If they report that they meet the eligibility requirements, they will be taken to an HIV tester at Prevention Point Philadelphia for confirmation of status. If a woman tests positive for HIV, she will be provided regular counseling through PPP's testing program and given access to resources and services to link her to immediate care. If the woman does not have HIV and is eligible to be in the study, she will be consented into the study.

Once confirmed to be HIV-, participants will be randomized to a group using REDCap's randomization tool and a baseline survey will be conducted by research staff. All survey assessments will be orally administered to participants to address any literacy or cognitive issues. Responses will be entered into REDCap by a research staff member.

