Participants will also continue to be monitored by the physician at Prevention Point. It is expected that a blood test or urine sample measuring PrEP levels and an HIV screening test would be done at the beginning, mid-point and the end of the intervention. It will also be done three months after the intervention is over. This will provide biomedical adherence data and ensure that participants have remained HIV negative.

After the intervention is over, all study participants may continue their PrEP prescription and have it administered out of the medical clinic at Prevention Point. In addition, PrEP counselors will remain available for participants should they have any further questions. Specialized counseling and text messages will no longer be provided. Three months after the intervention is over, we will contact participants to complete the last study assessment. This will be done at Prevention Point when the participant is there.

Instruments

There are five study assessments (See attachments). They include:

1. Eligibility Screener
2. Baseline Assessment
3. Mid-Intervention Assessment (in person and one question via text)
4. Post-Intervention Assessment
5. Three month follow-up Assessment

Analysis Plan

General - All data will be graphed and tabulated by treatment group for review of distributional properties and anomalous values prior to the main analyses. Continuous and normally distributed variables will be summarized with means and standard deviations. All parameter estimates will be bound by 95% confidence intervals and tests for differences in means and proportions will be deemed statistically significant $p < 0.05$. Post-hoc tests of significance will be based on adjustments for alpha to protect family-wise error rates at 5% using the method of Benjamini & Hochberg. For all analyses described in this study, we will use Statistical Analysis Software (SAS, version 9.4, Cary, N.C.).

Primary Outcome. The study's intent is to provide directional insight into the design of subsequent programmatic studies. As such, univariate group comparisons will be accomplished using an independent two-sample t-test for continuous measures (or non-parametric Wilcoxon

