statistic if the data is non-normally distributed) and chi-square test for categorical measures (or Fisher's Exact test if appropriate). Blood test results will also be compared to adherence benchmarks for Tenofovir-Emtricitabine and categorized as a binary variable (yes/no) based upon the mean value observed by all patients, with data at one month, three months and three months post intervention. We will use ANCOVA to assess differences between self-reported adherence and adherence as measured by blood test in the treatment group. Primary efficacy analyses will be a comparison of experimental to control group at one month, three months and three months post intervention, while other subgroup analyses based on race/ethnicity or age, for instance, as well as potential mediators and moderators, will be considered post-hoc exploratory analyses. In addition, logistic regression modeling will be used for binary adherence measures to assess group differences. Model assumptions will be tested, including linearity between the logit of the independent variables and the dependent, multicollinearity, and model misspecification.

Secondary outcomes. Secondary outcomes include self-efficacy, PrEP attitudes and decisional conflict. These measures are all continuous. Following evaluation of the primary outcome, we will explicitly examine the association between treatment adherence characteristics and extent of change among individuals in the treatment conditions in order to evaluate dose-response associations. Multiple linear models will be used to examine relationships between the groups and decisional conflict scale items, self-efficacy, and PrEP attitude scales at month three and three months post intervention. In these models, baseline outcome measures will be adjusted as covariate in the model development. PrEP attitudes will also be assessed through perceptual mapping analysis and compared from baseline to three month and three month follow-up for each group to assess "movement" toward adherence and away from negative perceptions of PrEP use. Promise of efficacy would indicate more movement by those in the "Enhanced" group compared to the "Basic" group. We will also explore potential mediators and moderators (HIV stigma, depression, level of drug use, social support). Outliers will be assessed using standardized residuals; if necessary, analyses will be accomplished for all data as well for non-outlying cases only.

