Acceptability and feasibility will be analyzed using survey items and objective measures (opened text messages, prescription pick-up). Quantitatively we will assess each feasibility and acceptability measure in both groups by inspecting trajectory plot of mean levels of satisfaction over time. No formal testing is proposed except for the descriptive statistics summarized at each follow-up assessment. We will also explore associations between participant characteristics and acceptability in order to identify subgroups of participants for whom the intervention may be less acceptable. Qualitative data will be collected via open-ended answers on the mid-intervention, post intervention and three month follow-up survey. This data will be analyzed using the Krueger method of analyzing narrative data. A thematic framework will be developed to create categories and quotes will be indexed according to categories to reduce data. Charting of quotes to enable analysis will then occur. These quotes, along with items with low mean ratings and those with the highest proportion of disagree and strongly disagree responses, will be used to assess acceptability and feasibility to inform development of a full-scale intervention.

Power calculations are not provided because we will be pilot testing a new intervention, and its effect size is not known. We have not fully powered the randomized test due to the study's size and purpose, which is to assess the feasibility, acceptability and promise of efficacy of the intervention, however with a projected n=25 in each group comparing adherence we have 80% power to detect an effect size of 0.79 (if it is a continuous measure) or an OR or 2.56 (if binary). Positive results will aid in our ability to further test the intervention in a fully powered randomized controlled trial and whether it is feasible in the context of offering it in a community-based, clinical setting.

Procedures Involved in Human Research

Description of Protocol

Consent Process

HRP-802=-Investigator Guidance Informed Consent will be followed to obtain informed consent. Before all assessments, a research staff member will review the written informed consent with the participants. Participants will have time to review the material and will be reminded that their participation is voluntary.

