Secondary outcomes. Secondary outcomes include self-efficacy, PrEP attitudes and decisional conflict. These measures are all continuous. Following evaluation of the primary outcome, we will explicitly examine the association between treatment adherence characteristics and extent of change among individuals in the treatment conditions in order to evaluate dose-response associations. Multiple linear models will be used to examine relationships between the groups and decisional conflict scale items, self-efficacy, and PrEP attitude scales at month three and three months post intervention. In these models, baseline outcome measures will be adjusted as covariate in the model development. PrEP attitudes will also be assessed through perceptual mapping analysis and compared from baseline to three month and three month follow-up for each group to assess "movement" toward adherence and away from negative perceptions of PrEP use. Promise of efficacy would indicate more movement by those in the "Enhanced" group compared to the "Basic" group. We will also explore potential mediators and moderators (HIV stigma, depression, level of drug use, social support). Outliers will be assessed using standardized residuals; if necessary, analyses will be accomplished for all data as well for non-outlying cases only.

Acceptability and feasibility will be analyzed using survey items and objective measures (opened text messages, prescription pick-up). Quantitatively we will assess each feasibility and acceptability measure in both groups by inspecting trajectory plot of mean levels of satisfaction over time. No formal testing is proposed except for the descriptive statistics summarized at each follow-up assessment. We will also explore associations between participant characteristics and acceptability in order to identify subgroups of participants for whom the intervention may be less acceptable. Qualitative data will be collected via open-ended answers on the mid-intervention, post intervention and three month follow-up survey. This data will be analyzed using the Krueger method of analyzing narrative data. A thematic framework will be developed to create categories and quotes will be indexed according to categories to reduce data. Charting of quotes to

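### Decisional conflict is named as one continuous secondary outcome, but the model sentence refers to its scale items; the total score should be named as the outcome modelled.

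*Combined protocol and SAP*

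**What the plan says.** The Specific Aim says the trial will "assess differences in self-reported PrEP attitudes, self-efficacy and decisional conflict", treating decisional conflict as a single construct. The Secondary outcomes paragraph of the Analysis Plan does the same: "Secondary outcomes include self-efficacy, PrEP attitudes and decisional conflict. These measures are all continuous".

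The model sentence in that paragraph uses a different unit. Linear models will "examine relationships between the groups and decisional conflict scale items, self-efficacy, and PrEP attitude scales at month three" and three months post intervention, with the baseline value of the outcome as covariate. The SAP repeats it: "relationships between the groups and decisional conflict scale items, self-efficacy, and PrEP attitude scales". Within the one list, PrEP attitudes enter as scales and decisional conflict as scale items.

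The General paragraph sets significance at p<0.05 and promises a Benjamini-Hochberg adjustment for post-hoc tests. The Primary Outcome paragraph applies the post-hoc label to subgroups, mediators and moderators. Neither paragraph extends the adjustment to the secondary models.

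The supplied text gives no item count, scoring rule or total score for decisional conflict. The surveys (Attachments E to H) and the outcomes list (Attachment I) are named but were not available for this review.

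**The concern.** The outcome definition and the model sentence point to different units of analysis. An analyst who follows the model sentence literally would produce a set of item-level results at each of two visits, each judged at p<0.05, and no single estimate for the outcome that the aim names.

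Two things are at stake. With many unadjusted item tests, some item will often look significant when nothing has changed. And if the unit stays open, the choice among a total, subscales or selected items can be made after the data are seen. Either would weaken the directional reading that the pilot is meant to hand on to a larger trial.

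**Working it through.** **Inputs from the documents.** Significance at p<0.05 (two-sided assumed; sidedness is not stated). Two visits for the secondary models. Sample size: "We aim to enroll 68 women, assuming a 75% retention rate at the end of the intervention, leaving us a final study sample of 50" (68 × 0.75 = 51, so about 25 per arm).

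**Inputs assumed, because the documents give none.** Item count k = 5, 10 or 16; inter-item correlation r = 0.3 to 0.5; correlation between visits 0.6; t-tests without baseline adjustment.

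**Step 1. The plan's own figure.** The plan states: "projected n=25 in each group comparing adherence we have 80% power to detect an effect size of 0.79 (if it is a continuous measure"). By normal approximation, power = Φ(0.79 × √(25/2) − 1.96) = Φ(2.793 − 1.960) = 79.8%. The noncentral t gives 78.1%. The figure reproduces. It is stated for adherence; none is given for decisional conflict.

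**Step 2. Number of tests.** Item by item, 2k tests: 10, 20 or 32. With a total score, 2.

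**Step 3. Chance of at least one p<0.05 under no effect, over both visits.** For independent tests it is 1 − 0.95^(2k). For correlated items it was simulated; the ranges cover r = 0.3 to 0.5 and differences between repeated simulations.

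| Items | Tests | Independent | Correlated items |
|---|---|---|---|
| 5 | 10 | 40.1% | 31-36% |
| 10 | 20 | 64.2% | 45-54% |
| 16 | 32 | 80.6% | 56-69% |
| Total score | 2 | 9.8% | about 8-10% |

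The total score is the right comparator. Tested at two visits, it also exceeds 5%.

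**Step 4. Power when all items shift together.** If each of k items shifts by d, the total shifts by d × √(k / (1 + (k−1)r)) in SD units. For k = 10 and d = 0.40:
- r = 0.3: 0.40 × √(10/3.7) = 0.40 × 1.64 = 0.66; power about 63%.
- r = 0.5: 0.40 × √(10/5.5) = 0.40 × 1.35 = 0.54; power 46%.
- A single item at 0.40: power 28%.

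Working back from a total-score effect of 0.79, with k from 4 to 16 and r from 0.3 to 0.7, a single unadjusted item has 36-67% power against 78% for the total (noncentral t).

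**Step 5. Power when few items shift.** If 3 of 10 items shift by 0.40, the total shifts by 3 × 0.40 / √(10 + 90r):
- r = 0.3: 1.2/√37 = 0.20; power about 10%.
- r = 0.5: 1.2/√55 = 0.16; power about 9%.

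Both are below the 28% for one affected item, so the advantage in Step 4 is conditional.

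**The case against.** The strongest reply is that the item wording may simply be loose. The same paragraph says of the three outcomes that "These measures are all continuous", other sections name decisional conflict as one construct, and the list is informal: self-efficacy carries neither the word scale nor the word items. Scoring may also be set out in the attachments. This stands. A reader might infer that the plan has settled on item-by-item models and excludes a total score, but no sentence says so.

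A reader might also infer a general loss of power. That does not hold either. Step 5 shows the total doing worse when few items move. The 28% for one item is also not the chance of seeing some signal: with all 10 items shifted by 0.40 SD, at least one is significant at a given visit in 74-85% of simulated trials, against 46-64% for the total. That higher figure comes with the false-positive rates in Step 3.

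Finally, the trial is a pilot with directional intent, the plan promises 95% confidence intervals for all estimates, and no stated decision rule rests on a decisional conflict p-value. Item results may also help in refining messages. This lowers the importance and supports still showing the items. It does not remove the mismatch between the outcome definition and the model sentence, and the repair is the same whichever reading was meant.

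**Conclusion.** The point holds as a mismatch within the plan: one continuous outcome is defined, while the literal model sentence works on its items, with no total score named in the supplied text and no multiplicity rule for the secondary models.

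If the wording is followed, the chance of at least one false-positive item over two visits is roughly 31-36% (5 items) to 56-69% (16 items), against about 8-10% for a total score. The sizes depend on the assumed item count and correlations and on unadjusted t-tests. The planned baseline adjustment would raise power for items and total alike, by an amount the documents do not allow one to compute. The power advantage of the total applies only when items shift together.

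The documents do not support saying that item-level modelling is a settled decision, or that power is lost whatever the pattern of effect. Importance is minor to moderate.

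**What to change.** In the Secondary outcomes paragraph of both the Analysis Plan and the SAP, replace the reference to decisional conflict scale items with the decisional conflict total score. Fit one linear model to it, adjusted for the baseline total, at month three and at three months post intervention. State the scoring rule or point to the attachment that holds it. Report the items descriptively by arm, without tests.

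The cost is one sentence in each place and no new data. The downside is that there are no item-level p-values and less sensitivity to a shift confined to a few items; the descriptive item table would still show such a pattern.

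### More perceptual-map movement in the Enhanced arm is read as promise of efficacy, with no measure of uncertainty and no rule for combining the two visits

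*Combined protocol and SAP*

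**What the plan says.** The Secondary outcomes paragraph appears in the protocol's Analysis Plan and again, in the same words, in the SAP. It names three outcomes: "Secondary outcomes include self-efficacy, PrEP attitudes and decisional conflict". PrEP attitudes are then analysed in two ways.

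- **Scales.** "Multiple linear models will be used to examine relationships between the groups" and the scale scores at month three and at the three-month follow-up, with the baseline value as a covariate.
- **Map.** Attitudes are also placed on a perceptual map and "compared from baseline to three month and three month follow-up for each group". Movement is described as a shift closer to adherence and further from unfavourable views of PrEP.

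The sentence that interprets the map is "Promise of efficacy would indicate more movement by those in the" Enhanced group than in the Basic group. It is worded in reverse; the evident meaning is that more movement in Enhanced would point to promise.

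The General paragraph states that "All parameter estimates will be bound by 95% confidence intervals" and that "tests for differences in means and proportions will be deemed statistically significant" at p < 0.05. It does not say how either rule would apply to a position on a map. The Specific Aim and Study Design sections tie the assessment of promise to adherence first, with attitudes, self-efficacy and decisional conflict alongside.

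**The concern.** The map sentence compares two group-level movements by size alone. Two finite samples never move by exactly the same amount, so one arm will always appear to have moved more, whether or not the targeted messages do anything. The plan gives no minimum difference, interval or between-arm test for the map, and no rule for the case where month three and follow-up point in different directions.

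What is at stake is a reporting error: a chance difference in map position could be written up as promise of efficacy. The map is a visible part of this project, because the Enhanced messages come from the same mapping and vector modelling. A favourable picture is therefore likely to be given weight. The plan also does not say which result governs if the map favours Enhanced while the linear model for the attitude scales shows nothing.

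**Working it through.** **Inputs from the documents.** The Sampling section assumes 75% retention of 68 women at the end of the intervention: 0.75 × 68 = 51, stated as 50. The power paragraph continues "with a projected n=25 in each group comparing adherence". The map is read at two visits, and no threshold is given. The documents do not describe how group movement is calculated.

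**Assumptions.** Tests are two-sided. Arms are exchangeable under no effect. Between-visit correlation is 0.5 to 0.7, with 0 to 0.9 as a wider range. For steps 4 and 5 only, movement is a per-participant score in SD units with 25 per arm.

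1. **The plan's own figure.** It reads "we have 80% power to detect an effect size of 0.79" for a continuous measure. By normal approximation the detectable effect is (1.960 + 0.842) × √(2/25) = 2.802 × 0.283 = 0.79, which reproduces it. The exact t-test gives 78.1% power at 0.79 and a detectable effect of 0.81. This figure concerns adherence; the documents give no operating figure for the map.

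2. **One visit, no effect.** Let D be movement in Enhanced minus movement in Basic. With exchangeable arms, D is symmetric about zero, so P(D > 0) = 0.50. A simulation of 200,000 trials at 25 per arm gave 0.50, both for movement along a fixed direction and for three-dimensional distance, with or without a shift common to both arms.

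3. **Two visits, no effect.** For a bivariate normal pair with correlation ρ, P(both > 0) = 1/4 + arcsin(ρ)/(2π). By symmetry P(neither > 0) is the same, so P(either > 0) = 1 − P(both > 0).

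| ρ | both visits favour Enhanced | at least one does |
|---|---|---|
| 0 | 0.250 | 0.750 |
| 0.5 | 0.250 + 0.083 = 0.333 | 0.667 |
| 0.7 | 0.250 + 0.123 = 0.373 | 0.627 |
| 0.9 | 0.428 | 0.572 |

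4. **How much a favourable reading tells us.** The SE of D is √(2/25) = 0.283 SD. At a true effect of 0.2 SD, P(D > 0) = Φ(0.2/0.283) = 0.76; at 0.5 SD it is 0.96. A favourable reading is thus only 0.76/0.50 = 1.5 times as likely under a true 0.2 SD effect as under none.

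5. **With an interval.** The 95% half-width is 1.96 × 0.283 = 0.55 SD. A two-sided 95% interval lies wholly above zero in 2.5% of trials with no effect, and in about 41% at a true effect of 0.5 SD.

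6. **Definition of movement.** If movement were read as raw distance travelled, unequal retention would tilt the reading toward the smaller arm, because its mean is noisier. Enhanced would move more in 54-58% of no-effect trials with 22 against 28 women, and in 43-46% with 28 against 22. Directional movement stays at 50% in both cases.

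**The case against.** The case for leaving the text alone has real force.

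- **The map is not the main test of promise.** The Specific Aim and Study Design rest promise mainly on adherence, and those comparisons have named tests.
- **The construct is already analysed formally.** The attitude scales go into baseline-adjusted models at the same two visits, under the general interval and significance rules.
- **The sentence may be only an expectation.** Read literally, it says that promise would show itself as more movement, not that any excess proves promise.
- **This is a pilot.** It seeks directional insight and says it is not fully powered. Requiring an interval to exclude zero would miss a true 0.5 SD effect more often than not.

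All four limit the point, and the last rules out a pass/fail bar as the remedy. Three stronger readings are also tempting and should be resisted.

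- A reader might infer that an ineffective intervention would be taken forward as often as a coin toss. The documents do not support this: the power paragraph says that positive results would help justify a larger trial, but does not make the map sufficient for that.
- A reader might quote only the 63-67% figure. It needs an either-visit rule that the plan does not state; an equally unstated both-visits rule gives 33-37%.
- A reader might say that the map breaks the plan's own 95% interval rule. If movement counts as a parameter estimate, an interval is already promised; if not, none is owed. The gap is that the text gives no method and the map sentence does not refer to one.

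The objection does not remove the label. Where the plan wants description only, as for acceptability and feasibility, it says that no formal testing is proposed. The map has no such statement and is attached to promise of efficacy instead.

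**Conclusion.** The point holds in limited form. As written, the map reading cannot separate an effect from chance: with no effect it favours Enhanced half the time at a single visit, whatever the sample size, provided the arms are exchangeable. The two-visit rates depend on a combining rule that the plan lacks and on correlations that are assumed. Even so, every rate in the table is far above the plan's 5% level.

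The consequence is confined to a supplementary reading of one secondary outcome and says nothing about the false-positive rate of the adherence comparisons or the linear models. It is worth correcting because a chance difference could otherwise be reported as promise, and the correction uses data already planned.

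**What to change.** Change the Secondary outcomes paragraph in both the protocol and the SAP:

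1. Define movement as the between-arm difference in change from baseline toward the adherence vector, so that it is directional and not raw distance.
2. Name one visit for this reading, or state how month three and the follow-up combine.
3. Report the difference with a permutation p-value from shuffling arm labels, or with a bootstrap 95% interval from resampling women within arm and rebuilding the map.
4. Replace the promise-of-efficacy sentence. Greater movement in Enhanced should be called directional and supportive only, read with its interval and the linear-model result for the attitude scales, and not taken as promise by itself.

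The cost is a short text change and some computing, with no new data. The computing is not trivial: maps rebuilt across resamples must be aligned to a common set of axes and vectors, and the documents do not yet describe the mapping procedure. The interval will also be wide at 25 per arm, and wider if fewer women remain at follow-up, so it will often include zero even when the messages have some effect. That is why step 4 asks for a supportive reading and not a threshold.
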